3.4. Enrollment Strategy

Study subjects will be recruited from the Institution/clinical site's subject database and/or utilizing Independent Ethics Committee (IEC) or Institutional Review Board (IRB) approved materials.

4. STUDY DESIGN AND RATIONALE

4.1. Description of Study Design

This study is a randomized, 5-visit, partial subject-masked, 2×3 bilateral crossover, dispensing trial. Both study lenses will be worn as daily wear (DW) for a period of 2 weeks each, and each study lens is expected to be worn at least five (5) days per week for at least six (6) hours per day worn. There will be no washout period between study lenses.

4.2. Study Design Rationale

Crossover designs are a well-established study design in which subjects are exposed to multiple treatments during different time periods. This design was considered since the study period is relatively short the design can be cost effective and more efficient comparisons between treatments can be made than compared a parallel study since fewer subjects are required to achieve the same pre-specified statistical power. [REDACTED]

[REDACTED] significant carryover effects were observed when assessing clinically relevant differences between the Test lens and a comparator while using a 2×2 crossover study design. Therefore this study utilizes a 3-period

by 2-treatment in order to estimate the true effect of the Test lens without any potential bias from the carry-over effect.

4.3. Enrollment Target and Study Duration

Approximately 130 subjects will be enrolled to ensure that at least 120 subjects will complete the study. Enrolled subjects will be habitual wearers of spherical contact lenses. All subjects will be the age of 18 and ≤ 49 years old. Eligible presbyopes will be those that wear full distance contact lenses in both eyes, then wear reading glasses over them. Subjects will wear the Test and Control contact lenses bilaterally approximately 2 weeks each on a daily wear (DW) basis, then wear either the Test or Control lens again for 2 weeks, for a total study duration of approximately 42 days (6 weeks) per subject.

5. TEST ARTICLE ALLOCATION AND MASKING

5.1. Test Article Allocation

This is a multi-site, partially-subject masked (control lens only) and randomized study. The study lenses will be worn in a bilateral and random fashion using a 2 treatment by 3 period (2×3) crossover design.

Permuted block randomization will be used to minimize the potential for treatment imbalance. A block size of two (2) sequences will be utilized. A computer-generated randomization scheme will be used to randomly assign subjects to one of the two possible lens wear sequences (TEST/CONTROL/CONTROL or CONTROL/TEST/TEST). The random scheme will be generated using the PROC PLAN procedure from SAS Software Version 9.4 or higher (SAS Institute, Cary, NC).

The study site must follow the randomization scheme provided and complete enrollment according to the randomization list and not pre-select or assign subjects. The randomized assignment of subjects will be performed at the first visit prior to the first fitting. The following must have occurred prior to randomization:

- Informed consent has been obtained
- Subject meets all the inclusion / exclusion criteria
- Subject history and baseline information has been collected

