5.2. Masking

Complete masking is impossible due to the functioning nature of the Test lens. The control lens will be over-labeled to mask the identity since the control lens may be the subject's habitual lens by chance. Therefore the study is partially-subject masked (control lens only).

Under normal circumstances, the mask should not be broken until all subjects have completed the study and the database is finalized. Otherwise, the mask should be broken only if specific emergency treatment/course of action would be dictated by knowing the treatment status of the subject. In such cases, the investigator may in an emergency contact the medical monitor. In the event the mask is broken, the sponsor must be notified before the

mask is broken. The date, time, and reason for the unmasking must be documented in the source document. The investigator is also advised not to reveal the study treatment assignment to the study site or sponsor personnel.

Subjects who have had their treatment assignment unmasked are expected to return for all remaining scheduled evaluations. Subjects who are discontinued may be replaced.

Use of the test articles will be randomized using a randomization scheme supplied by the study biostatistician.

If the test article is randomized, the order will be based on the randomization scheme assigned to the study site. The study site will follow the randomization scheme provided and will complete enrollment according to the randomization list and will not pre-select or assign subjects.

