5.3. Procedures for Maintaining and Breaking Randomization Codes

The test articles mask shall not be broken unless information concerning the lens type is necessary for the urgent medical treatment of a subject. The Sponsor must be notified before the mask is broken.

When dispensing test articles, the following steps should be followed to maintain randomization codes:

1. Investigator or designee (documented on the Delegation Log) will consult the lens fitting schedule/randomization scheme to obtain the test article assignment for that subject prior to dispensing
2. Investigator or designee will record the subject's number on the appropriate line of the randomization scheme
3. Investigator or designee will pull the appropriate test articles from the study supply. All test articles that are opened, whether dispensed (placed/fit on eye or dispensed outside the clinical site) or not, must be recorded on the Test Article Accountability Log in the "Dispensed" section

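### Blocks of two on a scheme held at the site make about half of the sequence assignments predictable; the consequence is modest and the remedy is cheap.

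*Combined protocol and SAP*

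**What the plan says.** Section 5.1 uses permuted blocks to "assign subjects to one of the two possible lens wear sequences (TEST/CONTROL/CONTROL or CONTROL/TEST/TEST"), and adds: "A block size of two (2) sequences will be utilized". Section 5.2 says that "the order will be based on the randomization scheme assigned to the study site", so I read the blocks as running within a site.

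Section 5.3 sets out the working procedure. The investigator or a delegate "will consult the lens fitting schedule/randomization scheme to obtain the test article assignment for that subject prior to dispensing". Then: "Investigator or designee will record the subject's number on the appropriate line of the randomization scheme". The same person pulls the lenses from stock. This describes a list with several lines, held and completed at the site.

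On masking, Section 5.2 states: "Complete masking is impossible due to the functioning nature of the Test lens". Only the Control lens is over-labeled, and only towards the subject. Section 5.2 also advises the investigator not to disclose assignments to the study site, which does not fit with Section 5.3, where site staff read them.

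There are two safeguards. One is an instruction, given in Section 5.1 and repeated in substance in Section 5.2: "The study site must follow the randomization scheme provided and complete enrollment according to the randomization list and not pre-select or assign subjects". The other is that consent, eligibility and baseline data must come before assignment. Envelopes, central release and varying block sizes are not mentioned.

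**The concern.** With two sequences and blocks of two, anyone who has seen an odd-numbered assignment at a site knows the next one. Staff see every assignment they make, and the block size is printed in the protocol they hold. Section 3.4 allows recruitment from the site's own subject database, so staff may know something of a patient's lens history before booking. The order of booking is then enough to influence who receives which sequence. The instruction not to pre-select and the eligibility-first rule are proper, but neither hides the next assignment.

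What is at stake is the comparability of the two sequence groups. Fit acceptance is where this bears most directly. It is a primary endpoint, tested against a fixed 90%, with no Control comparison to cancel a difference between groups. The sequence also decides how often the Test lens is worn.

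**Working it through.** The plan gives no predictability figure to reproduce.

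**Inputs.** Block size 2 and two sequences (Section 5.1). About 130 subjects: "Approximately 130 subjects will be enrolled to ensure that at least 120 subjects will complete the study" (Section 4.3). Five sites (site index in the Section 14.5 models). Fit assessment steps from Section 7.2.

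**1. Share of assignments that are certain.** Enumerating all 1:1 permuted blocks of size 2m, the share fixed by earlier places in the block is 1/(m + 1). The last column is for someone who always guesses the sequence with more places left.

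| Block size | Certain | Guessed correctly |
|---|---|---|
| 2 | 1/2 = 50% | 75% |
| 4 | 1/3 = 33% | 70.8% |
| 6 | 1/4 = 25% | 68.3% |

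With blocks of two, at most 130/2 = 65 assignments are certain. Each site that stops mid-block reduces the number of completed pairs. If all five did, the share would be (130 − 5)/2 ÷ 130 = 48.1%. With exactly 130 subjects at most four sites can have an odd count, which gives (130 − 4)/2 = 63, or 48.5%. The range is therefore about 48–50%.

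**2. Effect on the Test fit rate.** Test-lens fit assessments per completing subject:

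- TCC (Test in period 1): steps 1.23, 2.8 and 3.9, so 3 assessments in 1 period.
- CTT (Test in periods 2 and 3): steps 3.22, 4.9, 4.22 and 5.8, so 4 assessments in 2 periods.

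Suppose the sequence groups are equal in size and steering leaves the overall pool unchanged, so that the fit rates are r − d/2 in TCC and r + d/2 in CTT. A simple pooled Test rate then differs from r by:

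- by visit: d × (4/7 − 1/2) = d/14
- by period: d × (2/3 − 1/2) = d/6

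For an assumed d of 2 points this is 0.14–0.33 points; for 5 points it is 0.36–0.83. For scale, the planning rate of 95% in Section 14.2 lies 5 points above the 90% bar.

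**3. Effect on comfort.** I took the Section 14.2 covariance (202 on the diagonal, 105 off it) with 60 subjects per sequence, omitted baseline and site, and read the coefficient prior N(0, 1000) as variance 1000. The table shows the shift in the lens effect when CTT subjects score 1 point higher in every period.

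| Mean model | Shift per point |
|---|---|
| One lens effect, period, carryover, ordinary sequence term | about 0.00 |
| The same without a sequence term | +0.09 |
| Section 14.5 as printed | −0.03 to −0.04 |
| As printed, sign of the period-3 carryover term reversed | +0.43 to +0.45 |
| Period-specific lens effects, no sequence or carryover term | +0.33 |

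The printed model has 8 mean parameters for 6 sequence-by-period means (rank 6). Its average lens effect has a posterior SD of about 11–13 points, so the priors drive that result.

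**The case against.** The strongest reply is that this is a crossover: every subject wears both lenses, and a constant difference between subjects cancels within subject. That largely stands. With a conventional model and an ordinary sequence term, the comfort effect does not move. The planned comfort model also adjusts for baseline CLUE comfort, which would absorb part of any steering towards easier wearers. The fit model includes period, sequence and carryover terms, so the simple pooled calculation is only a guide. The protocol also forbids pre-selection and requires eligibility before assignment. What this reply does not reach is the Test-only fit rate, or the fact that the next assignment is not hidden.

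A reader might infer more than the documents support:

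- **That at least half, or even all, of the assignments are known in advance.** That requires staff to read later lines of the list. Section 5.3 does not exclude it, but nothing says that they can. Block inference alone gives at most half.
- **That steering would shift comfort towards Test by a third of the sequence difference.** This follows from averaging three between-group period contrasts, (−δ + δ + δ)/3. It holds only if the sequence and carryover terms printed in Section 14.5 are dropped. As printed, the shift is slightly negative and set by the priors.
- **That unmasked grading of fit and slit lamp findings is part of this point.** Assessor bias is a separate matter, and changing the block size or the release of assignments would not alter it.

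**Conclusion.** The point holds as a weakness in allocation concealment with a modest consequence. About half of the sequence assignments (48–50%) can be known in advance by block inference alone, assuming that blocks run within site and that there are five sites. The share would be larger if later lines of the scheme were readable, which the documents do not state. Only the sequence can be steered.

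The one consequence I can size is for fit acceptance: about 0.4–0.8 points on a simple pooled Test rate, if the sequences differed by an assumed 5 points. For comfort and acuity no reliable figure can be given, because the answer changes size and sign with the way the sequence and carryover terms are written. That is a model-specification question in its own right. Nothing in the documents suggests that selection occurred. The case for acting is that concealment cannot be restored after enrollment and that the change costs little.

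**What to change.** Regenerate the PROC PLAN list within site with randomly varying blocks of 4 and 6, and remove the block size from the protocol given to sites. Edit Sections 5.1 and 5.3 so that each assignment is released one at a time, after eligibility is recorded. Sealed numbered envelopes would do, or the EDC system if it can release assignments; Section 15.1 describes it for data capture only. The advice in Section 5.2 about not disclosing assignments to the site should be reconciled with Section 5.3 in the same edit.

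Larger blocks help only if upcoming lines are hidden, so both parts are needed.

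Cost: one new list, edits to the allocation sections, and minor set-up of envelopes or electronic release. Sequence imbalance within a site could reach 3 subjects instead of 1, which is small against an average of about 130/5 = 26 per site.

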5.2. Masking

Complete masking is impossible due to the functioning nature of the Test lens. The control lens will be over-labeled to mask the identity since the control lens may be the subject's habitual lens by chance. Therefore the study is partially-subject masked (control lens only).

Under normal circumstances, the mask should not be broken until all subjects have completed the study and the database is finalized. Otherwise, the mask should be broken only if specific emergency treatment/course of action would be dictated by knowing the treatment status of the subject. In such cases, the investigator may in an emergency contact the medical monitor. In the event the mask is broken, the sponsor must be notified before the

mask is broken. The date, time, and reason for the unmasking must be documented in the source document. The investigator is also advised not to reveal the study treatment assignment to the study site or sponsor personnel.

Subjects who have had their treatment assignment unmasked are expected to return for all remaining scheduled evaluations. Subjects who are discontinued may be replaced.

Use of the test articles will be randomized using a randomization scheme supplied by the study biostatistician.

If the test article is randomized, the order will be based on the randomization scheme assigned to the study site. The study site will follow the randomization scheme provided and will complete enrollment according to the randomization list and will not pre-select or assign subjects.

5.3. Procedures for Maintaining and Breaking Randomization Codes

The test articles mask shall not be broken unless information concerning the lens type is necessary for the urgent medical treatment of a subject. The Sponsor must be notified before the mask is broken.

When dispensing test articles, the following steps should be followed to maintain randomization codes:

1. Investigator or designee (documented on the Delegation Log) will consult the lens fitting schedule/randomization scheme to obtain the test article assignment for that subject prior to dispensing
2. Investigator or designee will record the subject's number on the appropriate line of the randomization scheme
3. Investigator or designee will pull the appropriate test articles from the study supply. All test articles that are opened, whether dispensed (placed/fit on eye or dispensed outside the clinical site) or not, must be recorded on the Test Article Accountability Log in the "Dispensed" section

6. STUDY INTERVENTION

6.1. Identity of Test Articles

The following contact lenses will be used in this study:

Table 1: Test Articles

	Control	Test
Name	OASYS	ECL100
Manufacturer	JJVC	JJVC
Compass Protocol(s) and/or Lot Number or Other Identifier	NA (Commercial Product)	[REDACTED]
Lens Material	senofilcon A	senofilcon A
Nominal Base Curve @ 22°C	8.4	8.4
Nominal Diameter @ 22°C	14.0	14.0
Nominal Distance Powers (D)	-1.00 to -6.00 in 0.25 steps	-1.00 to -6.00 in 0.25 steps
Water Content (Optional)	38	38
Center Thickness (Optional)	0.070	0.085
Oxygen Permeability (Dk)	103	103
Modality in Current Study	Daily wear	Daily wear
Replacement Frequency	Single use	Single use
Packaging Form (vial, blister, etc.)	Sterile blister pack	Sterile blister pack
New-UV blocker concentration	NA	~1.0%

Approximately 75 lenses per sku will be made available based on the following factors: sample size, 2x3 design, bilateral wear, biweekly replacement, safety margin of 2x, and US distribution model for the range of lenses -1.00 through -6.00 D.

6.2. Ancillary Supplies/Products

The following solutions will be used in this study:

Table 2: Ancillary Supplies

	Solution 1	Solution 2
Solution Name / Description	Opti-Free® PureMoist®	Eye-Cept® Rewetting Drops
Lot Number or Other Identifier	Varies	Varies
Manufacturer	Alcon Laboratories, Fort Worth, TX	Optics Laboratories
Maximum Preservative	0.001% polyquaternium-1, 0.0006% myristamidopropyl dimethylamine	NA

6.3. Administration of Test Articles

[figure not shown]
Test articles will be dispensed to subject meeting all eligibility requirements, including any dispensing requirements set forth in this clinical protocol. Subjects will be dispensed an adequate supply of test articles to complete the study. Lost or damaged test articles may be replaced at the discretion of the Investigator and/or the Sponsor.

6.4. Packaging and Labeling

The Test articles will be packaged in blisters as the primary packaging. The Control article will be over-labeled to mask the subject to the identity of the lens. The Test articles will be in

investigational cartons sealed with a tamper evident seal, commercial cartons, or in plastic bags as the secondary packaging form. The sample study label is shown below:

US label A (for control lens over-label)

6.5. Storage Conditions

Test articles will be maintained at ambient temperatures at the clinical site. Test articles must be kept under secure conditions and out of direct sunlight.

6.6. Collection and Storage of Samples

All worn study lenses will be collected from the subject, placed in labeled glass vials with Opti-Free® Puremoist®, and stored refrigerated or frozen until they are shipped back to the Sponsor. The lenses will be shipped in special containers to keep the lenses refrigerated.

When possible, any lens or test article associated with an Adverse Events and/or a Product Quality Complaint must be retained and stored in a glass vial with moderate solution pending directions from the sponsor for potential return back to JJVC.

6.7. Accountability of Test Articles

JJVC will provide the Investigator with sufficient quantities of study articles and supplies to complete the investigation. The Investigator is asked to retain all lens shipment documentation for the test article accountability records.

Test article must be kept in a locked storage cabinet, accessible only to those assigned by the Investigator for dispensing. The Investigator may delegate this activity to authorized study site personnel listed on the Site Delegation Log. All test articles must be accounted. This includes:

1. What was dispensed for the subject for trial fitting, to wear out of the office, or issued for the subject to replace appropriately between visits
2. What was returned to the Investigator unused
3. The number and reason for unplanned replacements.

The Investigator will collect all unused test articles from the subjects at the end of the subject's participation. Subject returned unused test articles must be separated from the

clinical study inventory of un-dispensed test articles, and must be labeled with the subject number and date of return. Following final reconciliation of test articles by the monitor, the Investigator or monitor will package and return all unused test articles to JJVC.

If there is a discrepancy between the shipment documents and the contents, contact the study monitor immediately.

[REDACTED]: Site Instructions for Test Article Receipt and Test Article Accountability for additional information.

7. STUDY EVALUATIONS

7.1. Time and Event Schedule

Table 3: Time and Events

Procedure	Baseline	Trial Fit & Dispense	Follow-up	Unsched	Exit
Visit	1	1, 3, 4	2, 3, 4, 5	PRN	5
Visit Window	-	-	6-8 Days 13-15 Days	-	-
Informed consent	✓	-	-	-	-
Eligibility screening	✓	-	-	-	-
CLUE Baseline Questionnaire	✓	-	-	-	-
GSI Background Questionnaire					
Other Questionnaires	✓	-	✓	-	-
Subject demographics	✓	-	-	-	-
General health and medication history	✓	-	-	-	-
Subject's own contact lens information	✓	-	-	-	-
Habitual lens care	✓	-	-	-	-
Entrance visual acuity	✓	-	-	-	-
Spherocylindrical refraction and BVA	✓	-	-	✓	✓
Slit lamp biomicroscopy	✓	-	✓	✓	-
Expanded Conjunctival Redness	✓	-	✓	✓	-
Expanded Corneal Staining	✓	-	✓	✓	-
Trial fitting lens information	-	✓	-	-	-
Lens Damage	-	✓	-	-	-
Distance spherical over-refraction	-	✓	✓	-	-
Lens modification	-	✓	-	-	-
Visual acuity	-	✓	✓	✓	-
Lens fitting assessment	-	✓	✓	*	-

Procedure	Baseline	Trial Fit & Dispense	Follow-up	Unsched	Exit
Visit	1	1, 3, 4	2, 3, 4, 5	PRN	5
Visit Window	-	-	6-8 Days 13-15 Days	-	-
Lens wettability	-	✓	✓	*	-
Lens dispensing information and criteria	-	✓	-	-	-
Patient instructions	-	✓	-	-	-
Lens information	-	-	✓	✓	-
Compliance	-	-	✓	✓	-
Wearing times	-	-	✓	✓	-
CLUE Follow-Up Questionnaire	-	-	✓	*	-
GSI Product Performance Questionnaire	-	-	✓	*	-
Symptoms	-	✓	✓	✓	-
Lens preference	-	-	V 2, 3, 4	-	-
Surface characteristics	-	-	✓	*	-
Chief complaint, diagnosis, treatment	-	-	-	✓	-
* if wearing study contact lenses					

7.2. Detailed Study Procedures

VISIT 1

Note that the subject must be wearing their habitual soft contact lenses into Visit 1.

Visit 1: Screening			
Step	Procedure	Details	
1.1	Statement of Informed Consent	Each subject must read, understand, and sign the Statement of Informed Consent before being enrolled into the study. The Principal Investigator or his/her designee conducting the informed consent discussion must also sign the consent form. Note: The subject must be provided a signed copy of this document.	
1.2	Demographics	Record the subject's date of birth, gender, race and ethnicity.	
1.3	Medical History and Concomitant Medications	Questions regarding the subjects' medical history and concomitant medications.	

1.4	Habitual Lenses	Questions regarding the subject's habitual lens type and parameters.	
1.5	Eligibility after Screening	All responses to Screening Inclusion Criteria questions must be answered "yes" and all responses to Exclusion Criteria must be answered "no" for the subject to be considered eligible.	

Visit 1: Baseline			
Step	Procedure	Details	
1.6	Baseline Questionnaires	
The subject will respond to the following questionnaires:
 
 1. CLUE Baseline Questionnaire 2. GSI Background Questionnaire 	
1.7	Other Questionnaires	
The subject will respond to additional questionnaires:
 
 1. Activity History 	
1.8	Entrance Visual Acuity	
Record the distance Snellen visual acuity (OD, OS, and OU) to the nearest letter with their habitual contact lens correction in place. Subjects must read the smallest line until at least 50% of the letters are read incorrectly.
	
1.9	Remove Habitual Lens	
The subject's habitual lenses will be removed and stored in their own lens case. If they forgot to bring their lens case, one will be provided to them.
	
1.10	Slit Lamp Findings	
FDA Slit Lamp Classification Scale (███████████ will be used to grade the findings and will be used to determine eligibility. Record only whole numbers. If any of these slit lamp findings are Grade 3 or higher, the subject is ineligible to continue but may return at a later date to complete another Baseline. If after a total of 2 attempts the subject is deemed ineligible, then complete the Final Evaluation.
 
Limbal and Bulbar Conjunctival Hyperemia findings ██████████ using the 0.5 increment scale, and Corneal Staining Assessment ██████████ will be emphasized using the 1.0
	

Visit 1: Baseline		
Step	Procedure	Details
		increment scale for internal purposes only.
1.11	Iris Color	The investigator will record the subject's iris color based on the scale provided.
1.12	Subjective Refraction	The investigator will complete a subjective refraction (sphere and cylinder) and record the resultant distance visual acuity OD, OS, and OU to the nearest letter. Best corrected distance visual acuity (BVA) must be 20/25+3 or better in each eye.
1.13	Eligibility after Baseline	All responses to Inclusion Criteria questions must be answered "yes" and all responses to Exclusion Criteria questions must be answered "no" for the subject to be considered eligible.
1.14	Eye Rinse	The study coordinator, investigator, or technician will rinse the subject's eyes thoroughly with saline.

Visit 1: Treatment 1 Lens Fitting		
Step	Procedure	Details
1.15	Lens Selection	Assign the study lens based on the randomization scheme. Select the contact lens power based on subjective best sphere refraction.
1.16	Lens Insertion	The Investigator or the subject inserts the study lenses. Record the time of lens insertion. Check for lens damage under the slit lamp before proceeding with lens settling. Replace damaged lenses if applicable.
1.17	Lens Settling	Allow the study lenses to settle for a minimum of 5 minutes.
1.18	Subjective Best Sphere Over Refraction and Modification	Perform a spherical over-refraction OD and OS. Optimize the lens power to achieve an over-refraction of ± 0.00 D OD and OS. Ensure that any new lenses are not damaged. One modification attempt will be allowed.

Visit 1: Treatment 1 Lens Fitting		
Step	Procedure	Details
1.19	Time Interval	Please wait for at least 10 minutes from final lens insertion to continue.
1.20	Subject Reported Ocular Symptoms	Subjects will respond to a verbal open-ended symptoms questionnaire.
1.21	Visual Acuity	Record the distance Snellen visual acuity with the contact lenses (OD, OS, and OU) to the nearest letter. Smaller lines must be shown until the subject incorrectly identifies at least 50% of the letters.
1.22	Distance ETDRS logMAR Visual Acuity	
Perform 4 m distance ETDRS logMAR visual acuity test OD and OS under the following conditions:
 
 • Bright illumination (e.g., >400 lux), with high contrast charts (HLHC); • The right eye will read Chart 1 • The left eye will read Chart 2
1.23	Subjective Lens Fit Assessment	
Subjective Assessment of the Lens Fit. If the fit is graded as unacceptable based on the criteria below, then the subject is discontinued from the study and will not be replaced.
 
 1. Limbal exposure in any gaze 2. Edge lift 3. Insufficient and/or excessive movement in all three movement categories
1.24	Continuance	
For the subject to continue in the study, they must meet all three of the following criteria:
 
 1. Snellen visual acuity is 20/30 or better OD and OS 2. The lens fit is acceptable OD and OS 3. Investigator approval. If the Investigator does not approve the dispensing of the first study lens, then the study is terminated for that subject.
1.25	Dispense	
The lenses will be dispensed for 6-8 days
 
 1. The subjects should wear their lenses similar to the inclusion criteria: ≥ 6 hours

Visit 1: Treatment 1 Lens Fitting		
Step	Procedure	Details
		
per day, ≥ 5 days per week.
 
 2. The lenses will be worn as daily wear only. 3. All subjects will be provided Opti-Free® PureMoist® to be used in a rub regime. 4. Preservative-free rewetting drops are permitted if needed. 5. A patient instruction booklet will be provided. 6. The lenses must be stored in the supplied case out of direct sunlight. 
Note 1: In the event a lens is lost or damaged, the subject will return to the investigator site for replacement (extra lenses cannot be given at the dispensing visit).
 
Note 2: The subject's habitual contact lenses cannot be worn at any time during the study.

VISIT 2

The follow-up will occur 6-8 days after the initial dispensing. The subjects must enter the visit wearing their study contact lenses.

Visit 2: Treatment 1 Follow-Up 1		
Step	Procedure	Details
2.1.	Adverse Events and Concomitant Medications Review	
Review the subject's concomitant medications and record any changes from the previous study visit.
 
Record any adverse events or medical history changes from the previous study visit.

2.2.	Wearing Time	Record the average wearing time and comfortable wearing time.
2.3.	Compliance	Confirm compliance with the prescribed wear schedule. Outdoor and total hours will be asked.
2.4.	Subject Reported Ocular Symptoms	Subjects will respond to a verbal open-ended symptoms questionnaire.
2.5.	Preference	Subjects will respond to a preference questionnaire comparing study lens 1 to their habitual lenses.

Visit 2: Treatment 1 Follow-Up 1		
Step	Procedure	Details
2.6.	Follow-Up Questionnaire	Subjects will respond to the following questionnaires: 1. CLUE Follow-up 2. GSI Product Performance
2.7.	Entrance Visual Acuity	Record the distance Snellen visual acuity with the contact lenses (OD, OS, and OU) to the nearest letter. Subjects must read the smallest line until at least 50% of the letters are read incorrectly.
2.8.	Subjective Lens Fit Assessment	Subjective Assessment of the Lens Fit. If the fit is graded as unacceptable based on the criteria below, then the subject is discontinued from the study and will not be replaced. 1. Limbal exposure in any gaze 2. Edge lift 3. Insufficient and/or excessive movement in all three movement categories
2.9.	Surface Deposits	Record any front and back surface lens deposits.
2.10.	Temporary Lens Removal & Storage	Both lenses will be removed and temporarily stored in a lens case with either saline or Opti-free® Puremoist®. The lenses will be reinserted in step 2.13.
2.11.	Slit Lamp Findings	Slit Lamp Classification Scale [REDACTED] will be used to grade the findings. Record only whole numbers. Limbal and Bulbar Conjunctival Hyperemia findings [REDACTED] and Corneal Staining Assessment [REDACTED] will be emphasized using a more detailed scale. Note: Findings must be Grade 2 or less as graded on the FDA scale [REDACTED] to continue onto Trial Period 2. If the subject is not eligible, they must be followed as an adverse event. Once resolved, the subject is terminated from the study. Adverse events must be reported to the JJVC monitors

Visit 2: Treatment 1 Follow-Up 1		
Step	Procedure	Details
		immediately.
2.12.	Eye Rinse	The study coordinator, investigator, or technician will rinse the subject's eyes thoroughly with saline.
2.13.	Lens Reinsertion	The lenses removed in step 2.10 will be reinserted. The subject will wear the same lenses an additional 6-8 days to their next scheduled visit.
2.14.	Exit Visual Acuity	Record the distance Snellen visual acuity with the contact lenses (OD, OS, and OU) to the nearest letter. Subjects must read the smallest line until at least 50% of the letters are read incorrectly.

VISIT 3

The follow-up will occur 6-8 days following Visit 2. The subjects must enter the visit wearing their study contact lenses.

Visit 3: Treatment 1 Follow-Up 2		
Step	Procedure	Details
3.1.	Adverse Events and Concomitant Medications Review	Review the subject's concomitant medications and record any changes from the previous study visit. Record any adverse events or medical history changes from the previous study visit.
3.2.	Wearing Time	Record the average wearing time and comfortable wearing time.
3.3.	Compliance	Confirm compliance with the prescribed wear schedule. Outdoor and total hours will be asked.
3.4.	Subject Reported Ocular Symptoms	Subjects will respond to a verbal open-ended symptoms questionnaire.
3.5.	Preference	Subjects will respond to a preference questionnaire comparing study lens 1 to their habitual lenses.

Visit 3: Treatment 1 Follow-Up 2			
Step	Procedure	Details	CTP
3.6.	Follow-Up Questionnaire	Subjects will respond to the following questionnaires: 1. CLUE Follow-up 2. GSI Product Performance	
3.7.	Visual Acuity	Record the distance Snellen visual acuity with the contact lenses (OD, OS, and OU) to the nearest letter. Subjects must read the smallest line until at least 50% of the letters are read incorrectly.	
3.8.	logMAR (ETDRS) Visual Acuity	Perform 4 m distance ETDRS logMAR visual acuity test OD and OS under the following conditions: 
• Bright illumination (e.g., >400 lux), with high contrast charts (HLHC);• The right eye will read Chart 1• The left eye will read Chart 2	
3.9.	Subjective Lens Fit Assessment	Subjective Assessment of the Lens Fit. If the fit is graded as unacceptable based on the criteria below, then the subject is discontinued from the study and will not be replaced. 1. Limbal exposure in any gaze 2. Edge lift 3. Insufficient and/or excessive movement in all three movement categories	
3.10.	Surface Deposits	Record any front and back surface lens deposits.	
3.11.	Lens Removal & Storage	Both lenses will be removed and stored wet in a labeled container with Opti-Free® PureMoist®. The lenses can be stored refrigerated or frozen prior to shipment back to the Sponsor. Lenses will be stored at JJVC for 45 days after LSLV for laboratory testing (Section 7.4).	
3.12.	Slit Lamp Findings	Slit Lamp Classification Scale [REDACTED] will be used to grade the findings. Record only whole numbers. Limbal and Bulbar	[REDACTED] [REDACTED]

Visit 3: Treatment 1 Follow-Up 2			
Step	Procedure	Details	CTP
		
Conjunctival Hyperemia findings and Corneal Staining Assessment will be emphasized using a more detailed scale.
 
Note: Findings must be grade 2 or less as graded on the FDA scale [REDACTED] to continue onto Trial Period 2. If the subject is not eligible, they must be followed as an adverse event. Once resolved, the subject is terminated from the study. Adverse events must be reported to the JJVC monitors immediately.
	[REDACTED]
3.13.	Eye Rinse	The study coordinator, investigator, or technician will rinse the subject's eyes thoroughly with saline.	

Visit 3: Treatment 2 Lens Fitting			
Step	Procedure	Details	
3.14.	Lens Selection	
Assign the study lens based on the randomization scheme.
 
Select the contact lens power based on subjective best sphere refraction.
	[REDACTED]
3.15.	Lens Insertion	
The Investigator or the subject inserts the study lenses. Record the time of lens insertion.
 
Check for lens damage under the slit lamp before proceeding with lens settling.
 
Replace damaged lenses if applicable.
	
3.16.	Lens Settling	Allow the study lenses to settle for a minimum of 5 minutes.	
3.17.	Subjective Best Sphere Over Refraction	Perform a spherical over-refraction OD and OS. Optimize the lens power to achieve an over-refraction of ± 0.00 D OD and OS. Ensure that any new lenses are not damaged. One modification attempt will be allowed.	
3.18.	Time Interval	Please wait for at least 10 minutes from final lens insertion to continue.	

Visit 3: Treatment 2 Lens Fitting		
Step	Procedure	Details
3.19.	Subject Reported Ocular Symptoms	Subjects will respond to a verbal open-ended symptoms questionnaire.
3.20.	Visual Acuity	Record the distance Snellen visual acuity with the contact lenses (OD, OS, and OU) to the nearest letter. Smaller lines must be shown until the subject incorrectly identifies at least 50% of the letters.
3.21.	Distance ETDRS logMAR Visual Acuity	
Perform 4 m distance ETDRS logMAR visual acuity test OD and OS under the following conditions:
 
 • Bright illumination (e.g., >400 lux), with high contrast charts (HLHC); • The right eye will read Chart 3 • The left eye will read Chart 4
3.22.	Subjective Lens Fit Assessment	
Subjective Assessment of the Lens Fit. If the fit is graded as unacceptable based on the criteria below, then the subject is discontinued from the study and will not be replaced.
 
 1. Limbal exposure in any gaze 2. Edge lift 3. Insufficient and/or excessive movement in all three movement categories
3.23.	Continuance	
For the subject to continue in the study, they must meet all three of the following criteria:
 
 1. Visual acuity is 20/30 or better OD and OS 2. The lens fit is acceptable OD and OS 3. Investigator approval. If the Investigator does not approve the dispensing of the first study lens, then the study is terminated for that subject.
3.24.	Dispense	
The lenses will be dispensed for 13-15 days.
 
 1. The subjects should wear their lenses similar to the inclusion criteria: ≥ 6 hours per day, ≥ 5 days per week. 2. The lenses will be worn as daily wear only. 3. All subjects will be provided Opti-Free®

Visit 3: Treatment 2 Lens Fitting		
Step	Procedure	Details
		
PureMoist® to be used in a rub regime.
 
4. Preservative-free rewetting drops are permitted if needed.
 
5. The lenses must be stored in the supplied case out of direct sunlight.
 
Note 1: In the event a lens is lost or damaged, the subject will return to the investigator site for replacement (extra lenses cannot be given at the dispensing visit).
 
Note 2: The subject's habitual contact lenses cannot be worn at any time during the study.

VISIT 4

The follow-up will occur 13-15 days after the dispensing of the second study lenses. The subjects must enter the visit wearing their study contact lenses.

Visit 4: Treatment 2 Follow-Up		
Step	Procedure	Details
4.1.	Adverse Events and Concomitant Medications Review	
Review the subject's concomitant medications and record any changes from the previous study visit.
 
Record any adverse events or medical history changes from the previous study visit.

4.2.	Wearing Time	Record the average wearing time and comfortable wearing time.
4.3.	Compliance	Confirm compliance with the prescribed wear schedule. Outdoor and total hours will be asked.
4.4.	Subject Reported Ocular Symptoms	Subjects will respond to a verbal open-ended symptoms questionnaire.
4.5.	Lens Preferences	Subjects will respond to the preference questionnaire comparing study lens 1 and study lens 2.
